3.2 Exclusion Criteria

- 1. Patient is known to be less than 18 years old.
- 2. Patient is known to be pregnant.
- 3. Patient is known to be a prisoner.
- 4. Immediate need for tracheal intubation precludes safe performance of study procedures.
- 5. Operator has determined that use of a video laryngoscope or use of a direct laryngoscope is required or contraindicated for the optimal care of the patient.

4 Consent

Use of a video laryngoscope and use of a direct laryngoscope are both common approaches to emergency tracheal intubation during emergency tracheal intubation in the ED and ICU. Both represent standard-of-care treatment in current clinical practice. Results from prior clinical trials are conflicting and do not demonstrate superiority of one approach over the other. Consequently, some guidelines do not strongly recommend for or against the use of a video laryngoscope or a direct laryngoscope on the first attempt at tracheal intubation of critically ill adults.¹⁷ As a result, significant variation exists in the use of a video laryngoscope vs use of a direct laryngoscope in current clinical practice.² This trial will only enroll patients who are undergoing emergency tracheal intubation as part of their clinical care for whom the treating clinicians feel that either a video laryngoscope or a direct laryngoscope would be consistent with the optimal care of the patient. We will request a waiver of informed consent because the study involves minimal incremental risk and obtaining informed consent would be impracticable.

Participation in this study involves minimal incremental risk because:

- Both approaches to tracheal intubation being compared are commonly used in routine clinical care;
- Both are interventions to which patients would be exposed even if not participating in the study (all patients undergoing laryngoscopy and tracheal intubation receive either a video laryngoscope or a direct laryngoscope);
- No established differences in risk and benefit are known to exist between the two approaches based on the currently available data; and
- Patients are only eligible to participate if their treating clinicians have determined that both approaches are acceptable for the optimal care of the patient.

Obtaining informed consent would be impracticable because:

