5.3.3 Handling of Patients Found to Be Prisoners after Enrollment

Prisoners typically present with obvious physical signs such as prison uniforms, handcuffs, and the presence of law enforcement. Training of treating clinicians and the enrollment procedures listed above (posting of inclusion and exclusion criteria alongside enrollment envelopes and a "pre-enrollment time-out" with verbal recitation of eligibility criteria) have proven to be effective in preventing the enrollment of prisoners in recent trials.

If a patient who presents to the ED or ICU is not known to be a prisoner at the time of enrollment and following enrollment is discovered to be a prisoner or becomes a prisoner between enrollment and the end of study follow up, all study procedures will stop immediately, the patient will be withdrawn from the study, and the patient's study record will be expunged of all study data except the anonymous study ID and randomized group assignment. Because both study interventions are one-time, standard-of-care

interventions which the patient was likely to receive in clinical care even if not participating in research, no further follow-up will occur.

6 Study Procedures

For enrolled patients, study group assignment determines only the choice of laryngoscope. Operators may opt to use the non-assigned laryngoscope type on the first laryngoscopy attempt if it is felt to be required for the safe care of the patient. The occurrence of such "crossover" event will be recorded along with the indication. All other aspects of the intubation procedure in both study groups will be at the discretion of the operator. For all patients in the trial, best practices in tracheal intubation will be encouraged according to clinical protocols in the study settings.

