For patients assigned to the video laryngoscope group, operators are instructed to use a video laryngoscope on the first laryngoscopy attempt. A video laryngoscope is defined as a laryngoscope with a camera and a video screen. Trial protocol does not dictate the brand of video laryngoscope or the geometry of the laryngoscope blade (e.g. hyperangulated vs. non-hyperangulated), but these details will be recorded. Operators are encouraged, but not required, to view the video screen during laryngoscopy ("indirect laryngoscopy") and tracheal intubation.

Direct Laryngoscope Group

For patients assigned to the direct laryngoscope group, operators are instructed to use a direct laryngoscope on the first laryngoscopy attempt. A direct laryngoscope is defined as a laryngoscope without a camera and a video screen. Trial protocol does not dictate the brand of direct laryngoscope or the geometry of the laryngoscope blade (e.g. curved [Macintosh] vs. straight [Miller]), but these details will be recorded.

Co-Interventions and Subsequent Attempts at Laryngoscopy and Intubation

Study group assignment determines only the type of laryngoscope (video vs direct) used on the first laryngoscopy attempt. If determined to be required to ensure optimal care of the patient, treating clinicians may use any device at any time, regardless of study group assignment. Cases in which clinicians use a laryngoscope discordant with randomized assignment on the first intubation attempt will be documented and tracked. All aspects of the

intubation procedure, except the type of laryngoscope used on the first attempt, are at the discretion of treating clinicians, including selection of sedative and neuromuscular blocking medications, patient positioning, approach to pre-oxygenation, use of a bougie or a stylet, and endotracheal tube size. Best practices in tracheal intubation will be encouraged according to clinical protocols at the study sites. The trial intervention ends after the first attempt at laryngoscopy. If the first attempt is unsuccessful, the operator may use any method of intubation on subsequent intubation attempts, including use of a direct laryngoscope in the video laryngoscope group or use of a video laryngoscope in the direct laryngoscope group. The type of laryngoscope used during the initial and final laryngoscopy attempt will be collected and reported.

Data Collection

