Analyses will be conducted following reproducible research principles using R (R Foundation for Statistical Computing, Vienna, Austria).⁴⁰ We will present summary tabulations by treatment group. For categorical variables, the number and proportion of patients will be presented. For continuous variables, the mean and standard deviation or median and interquartile range will be presented, as appropriate.

We will analyze a single pre-specified primary outcome and a single pre-specified secondary outcome using a chi-square test. Consistent with recommendations of the Food and Drug Administration⁴¹ and the European Medicines Agency⁴², each will be tested using a two-sided P value with a significance level of 0.05. The primary analysis will occur in an intent-to-treat fashion among all patients randomized, excluding only those patients whose data was withdrawn from the study. For all other analyses except safety analyses, emphasis will be placed on the estimate of effect size with 95% confidence intervals, as recommended by the *International Committee of Medical Journal Editors*⁴³, and no corrections for multiple comparisons will be performed.

Main Analysis of the Primary Outcome

The main analysis will be an unadjusted, intention-to-treat comparison of successful intubation on the first attempt between patients randomized to the video laryngoscope group and patients randomized to the direct laryngoscope group, using a chi-square test. The difference in proportions, the associated 95% confidence interval, and a p value for the primary outcome will be presented.

Secondary Analyses of the Primary Outcome

Multivariable modeling to account for covariates

To account for relevant covariates, we will develop a generalized linear mixed effects model using a logit link function with the primary outcome as the dependent variable, study site as a random effect, and fixed effects of study group and the following pre-specified baseline covariates: age, sex, body-mass index, operator experience quantified as the operator's total number of prior intubations, and location of intubation (ED vs ICU). All continuous variables will be modeled assuming a nonlinear relationship to the outcome using restricted cubic splines with between 3 and 5 knots.

Effect Modification

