Sensitivity Analyses of the Primary Outcome

We will assess the robustness of the findings of the primary analysis in a number of sensitivity analyses. First, because operators may choose to deviate from the assigned laryngoscope for the safety of the patient, we will repeat the primary analysis, but will consider patients for whom the operator crossed over on the first attempt from the assigned laryngoscope type to the non-assigned laryngoscope type not to have experienced successful intubation on the first attempt. Second, we will repeat the primary analysis among only patients

for whom data on the primary outcome from the independent observer is available (i.e., excluding cases in which operator self-report was the sole source of information for the primary outcome). Third, because the operator's prior experience with each type of laryngoscope may affect the likelihood of success with a video laryngoscope compared with a direct laryngoscope, we will repeat the primary analysis among only cases in which the proportion of prior intubations the operator has performed using a direct laryngoscope is between 0.25 and 0.75.

Analysis of the Secondary Outcome

For the secondary outcome, severe complications occurring between induction and 2 minutes following intubation, we will perform an unadjusted, intention-to-treat comparison of patients randomized to the video laryngoscope group versus patients randomized to the direct laryngoscope group, using a chi-square test.

Analyses of Exploratory Outcomes

For all pre-specified exploratory outcomes, we will conduct unadjusted, intention-to-treat analyses comparing patients randomized to the video laryngoscope group versus patients randomized to the direct laryngoscope group. We will calculate absolute risk differences or differences in medians between groups with the associated 95% confidence intervals.

Handling of Missing Data

We anticipate that no data on the primary outcome will be missing. When data are missing for the secondary or exploratory outcomes, we will perform complete-case analysis, excluding cases where the data for the analyzed outcome are missing. There will be no imputation of missing data for these outcomes. In adjusted analyses, missing data for covariates will be imputed using multiple imputations.

Trial status

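### Does counting every first-attempt crossover as a failure spoil the SAP's first sensitivity analysis?

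*SAP*

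**What the plan says.** The primary analysis is fixed in the SAP under Main Analysis of the Primary Outcome: "The main analysis will be an unadjusted, intention-to-treat comparison of successful intubation on the first attempt", by chi-square test.

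Under Sensitivity Analyses of the Primary Outcome the SAP states its aim: "We will assess the robustness of the findings of the primary analysis in a number of sensitivity analyses". The first of three is prompted by operators departing from the assigned device for safety. It reruns the primary analysis and takes patients who crossed over "from the assigned laryngoscope type to the non-assigned laryngoscope type not to have experienced successful intubation on the first attempt". The rule applies in both arms and in both directions.

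Crossover is permitted. Protocol Section 6 says "Operators may opt to use the non-assigned laryngoscope type on the first laryngoscopy attempt if it is felt to be required" for safe care, and has the event and its indication recorded. The SAP section on co-interventions adds "Cases in which clinicians use a laryngoscope discordant with randomized assignment on the first intubation attempt will be documented and tracked", and "The type of laryngoscope used during the initial and final laryngoscopy attempt will be collected and reported". Protocol Section 3.2 removes beforehand any patient for whom the operator judges that either device "is required or contraindicated for the optimal care of the patient".

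For analyses other than the primary and secondary tests, and safety analyses aside, the SAP says "emphasis will be placed on the estimate of effect size with 95% confidence intervals". Neither document gives an expected crossover rate, plans a per-protocol, as-treated or complier-average analysis, or explicitly promises first-attempt outcomes among crossovers by arm.

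**The concern.** A sensitivity analysis usually relaxes an assumption behind the main estimate. This one changes the outcome, from success on the first attempt to success on the first attempt with the assigned device. If more direct-arm patients are switched to video and intubated successfully than the reverse, the check moves toward video whatever the device effect. A reader who sees an ITT result favouring video, followed by a larger estimate labelled as a robustness check, could take it as added support. With crossover mainly in the other direction, a sound ITT result could look fragile.

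Because the plan stresses estimates and intervals, the moved estimate is what readers will see. That suggested three changes: call the analysis a supplementary composite, report crossovers and their successes by arm, and add a complier-average effect. At stake is how one secondary analysis is read, not the trial's main conclusion.

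**Working it through.** **Inputs from the documents.** Direct-arm success of 80%, a 5-point design difference (so 85% with video) and 1,000 patients per arm, all from the SAP's Sample Size Estimation. The documents give no crossover figure to reproduce. Every crossover rate, and every success rate among crossovers, below is an assumption.

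**Identity.** Let cD and cV be the shares of the direct and video arms that cross over on the first attempt, and sD and sV the first-attempt success rates among them. The check removes cD·sD successes from the direct arm and cV·sV from the video arm. Hence

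check (video minus direct) = ITT + cD·sD − cV·sV.

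Crossovers who fail contribute nothing.

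**Size of the shift**, in percentage points:

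| Direct / video crossover | 80% success | 60% success |
|---|---|---|
| 1% / 1% or 3% / 3% | 0 | 0 |
| 2% / 1% | +0.8 | +0.6 |
| 3% / 1% | +1.6 | +1.2 |
| 5% / 1% | +3.2 | +2.4 |
| 1% / 3% | −1.6 | −1.2 |

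For example, 0.03 × 0.80 − 0.01 × 0.80 = 0.016, which is 32% of the 5-point design difference.

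**What imbalance would matter.** Suppose ITT is exactly null at 800 per 1,000 in each arm. A net 37 successful direct-to-video crossovers gives 800 against 763. The pooled proportion is 0.7815, the standard error is √(0.7815 × 0.2185 × 2/1,000) = 0.0185, and z = 0.037/0.0185 = 2.0. At 80% success, 37 successes need about 37/0.80 = 46 net crossovers, or 4.6% of an arm.

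**Comparison with a complier-average effect.** Suppose a share cD receives video in either arm, a share cV receives direct in either arm, and the rest comply. Success is 85% on video and 80% on direct. At 3%/1%:

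- ITT = 0.96 × 0.05 = 0.0480.
- Shift = 0.03 × 0.85 − 0.01 × 0.80 = 0.0175, so the check = 0.0655.
- Complier-average effect = 0.0480/(0.99 − 0.03) = 0.0500.

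| Direct / video crossover | ITT | Planned check | Complier-average |
|---|---|---|---|
| 3% / 1% | 4.8 | 6.55 | 5.0 |
| 5% / 1% | 4.7 | 8.15 | 5.0 |
| 3% / 3% | 4.7 | 4.85 | 5.0 |
| 1% / 3% | 4.8 | 3.25 | 5.0 |

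The complier-average column is constant because the model builds in the assumptions that the method needs. At 3%/1% its 95% interval half-width is 3.5 points against 3.3 for ITT. In simulation its share of significant results stayed within 0.2 points of ITT. It is ITT divided by 0.96, with nearly the same test.

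**Can the shift be seen from what is already planned?** In the 3%/1% case the expected successes per 1,000 are as follows.

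- Direct arm, ITT: 25.5 + 8 + 768 = 801.5. Check: 801.5 − 25.5 = 776.
- Video arm, ITT: 25.5 + 8 + 816 = 849.5. Check: 849.5 − 8 = 841.5.

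Subtracting within each arm returns 25.5 and 8, the successful crossovers. The SAP's Statistical Analysis Principles promise tables by randomized group with counts and percentages, and first-attempt device type is to be reported. Tabulated by group, those give the crossover counts too.

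**The case for a change.** The strongest case for a change is that the label promises robustness while the arithmetic delivers a different outcome. The shift has no fixed sign, so the check is neither a conservative bound nor a test of an assumption behind ITT. It is also the only crossover analysis planned. The remedy is a short paragraph using data already collected. Protocol Section 9.4 treats analyses requested after enrollment is complete as post hoc, which favours acting early.

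The algebra stands, and so does its consequence: agreement between this check and ITT should not, alone, be read as robustness to crossover. The rest is weaker.

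- **Relabelling** changes no number. The rule is explicit, and the documents use no estimand framework that would require a distinction between sensitivity and supplementary analyses.
- **Crossover successes by arm** follow by subtraction from arm-level results. The SAP does not say outright that arm-level counts will accompany the sensitivity analysis, so a small reporting gap remains, of a kind analysts ordinarily fill. Such a table is descriptive and loses little if added late.
- **The complier-average effect** rests on two untestable assumptions: assignment acts only through the first-attempt device, and nobody would receive the opposite device under both assignments. As a rescaled ITT with essentially the same test, it supplies no independent evidence of robustness either. Setting 6.55 beside 5.0 also makes the check look biased, when it targets a different quantity.

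The larger shifts need threefold or fivefold imbalances that nothing in the documents supports. Excluding patients for whom either device is required or contraindicated may keep crossover low, though the documents do not show this.

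**Conclusion.** No change to the plan. The analysis is a clearly specified composite, success on the first attempt with the assigned laryngoscope, and treating abandonment of the assigned device as failure is a legitimate secondary question. Its difference from ITT is exactly the between-arm difference in the share of successful crossovers. That is zero when the arms balance, 0.8 points for 1% one-sided crossover at 80% success, and larger only with a marked imbalance. These sizes rest on assumed rates.

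Followed as written, the plan still gives a sound primary result, and the secondary outcome and interim stopping rule do not depend on this analysis. Readers should see it beside the crossover counts. Printing, by arm, the number of first-attempt crossovers and how many succeeded would be a helpful reporting courtesy. The new label and the complier-average effect are matters of preference, not corrections of an error.

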| Primary Outcome | Successful intubation on the first attempt , defined as the placement of an endotracheal tube in the trachea with a single insertion of a laryngoscope blade into the mouth and EITHER a single insertion of an endotracheal tube into the mouth OR a single insertion of a bougie into the mouth followed by a single insertion of an endotracheal tube over the bougie into the mouth. | |
| Secondary Outcome | Incidence of severe complications , defined as the occurrence of one or more of the following between induction and 2 minutes after intubation: [1] severe hypoxemia (SpO2 <80%), [2] severe hypotension (systolic blood pressure <65 mm Hg or new or increased vasopressor administration), [3] cardiac arrest not resulting in death within 1 hour of induction, or [4] cardiac arrest resulting in death within 1 hour of induction. | |
| Exploratory Outcomes | Procedural: Duration from laryngoscopy to tracheal intubation – defined as the interval (in seconds) between insertion of the laryngoscope into the mouth on the first laryngoscopy attempt and final placement of an endotracheal tube or tracheostomy tube in the trachea. Number of laryngoscopy attempts | |

| | Number of attempts to cannulate the trachea with a bougie Number of attempts to cannulate the trachea with an endotracheal tube Reason for failure to intubate on the first attempt Operator-reported aspiration into the airway Safety: Esophageal intubation Injury to the teeth Clinical: ICU-free days in the first 28 days Ventilator free days in the first 28 days 28-day, all-cause in-hospital mortality | |
|-------------------|---|--|
| Analysis | The primary analysis will be an intention-to-treat comparison of patients randomized to the video laryngoscope group versus patients randomized to the direct laryngoscope group with regard to the primary outcome of successful intubation on the first attempt. The difference in proportion and the associated 95% confidence interval will be presented. Between group differences will be examined using a Chi-square test. | |
| Sample Size | 2,000 patients | |
| Expected Duration | 18 months | |

1 Background

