7.2 Recorded Study Outcomes

7.2.1 Primary Outcome

The primary outcome is successful intubation on the first attempt. Successful intubation on the first attempt is defined as placement of an endotracheal tube in the trachea with a single insertion of a laryngoscope blade into the mouth and EITHER a single insertion of an endotracheal tube into the mouth OR a single insertion of a bougie into the mouth followed by a single insertion of an endotracheal tube over the bougie into the mouth.

The primary outcome will be collected by an observer trained in recording the number of insertions of the laryngoscope blade into the mouth and the number of insertions of a bougie and endotracheal tube into the mouth. If data on the primary outcome from the independent observer are missing, the operator's self-report of successful intubation on the first attempt will be used.

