7.2.3 Exploratory Outcomes

Exploratory procedural outcomes:

- Duration of laryngoscopy and tracheal intubation defined as the interval (in seconds) between the first insertion of a laryngoscope blade into the mouth and the final placement of an endotracheal tube or tracheostomy tube in the trachea.
- Number of laryngoscopy attempts
- Number of attempts to cannulate the trachea with a bougie or an endotracheal tube
- Successful intubation on the first attempt without a severe complication
- Reason for failure to intubate on the first attempt
 - Inadequate view of the larynx
 - Inability to intubate the trachea with an endotracheal tube
 - Inability to cannulate the trachea with a bougie
 - Attempt aborted due to change in patient condition (e.g., worsening hypoxemia, hypotension, bradycardia, vomiting, bleeding)
 - Technical failure of the laryngoscope (e.g., battery, light source, camera, screen)
 - o Other
- Operator-reported aspiration

Exploratory safety outcomes:

- Esophageal intubation
- Injury to the teeth

Exploratory clinical outcomes:

- ICU-free days in the first 28 days
- Ventilator free days in the first 28 days
- 28-day all-cause in-hospital mortality

8 Risks and Benefits

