Data for the assessment of the primary outcome are collected by a trained independent observer using a structured data collection form that records the number of insertions of the laryngoscope blade, bougie (if used), and endotracheal tube into the patient's mouth. In the event that data from the independent observer are missing, data from the operator's self-report of successful intubation on the first attempt will be used.

Secondary Outcome

The secondary outcome is the incidence of severe complications occurring between induction and 2 minutes following successful intubation. Severe complications are defined as one or more of the following:

- Severe hypoxemia (lowest oxygen saturation measured by pulse oximetry < 80%);
- Severe hypotension (systolic blood pressure < 65 mm Hg or new or increased vasopressor administration);
- Cardiac arrest not resulting in death
- Cardiac arrest resulting in death

Cardiac arrest will be considered to have resulted in death if a patient who experienced cardiac arrest between induction and 2 minutes after intubation died within the 1 hour following intubation.

Exploratory procedural outcomes are as follows:

- Duration of laryngoscopy and tracheal intubation. This is defined as the interval (in seconds) between the first insertion of a laryngoscope blade into the mouth and the final placement of an endotracheal tube or tracheostomy tube in the trachea.
- Number of laryngoscopy attempts
- Number of attempts to cannulate the trachea with a bougie or endotracheal tube
- Successful intubation on the first attempt without a severe complication
- Reason for failure to intubate the trachea on the first attempt, which include:
 - Inadequate view of the larynx
 - o Inability to intubate the trachea with an endotracheal tube
 - Inability to cannulate the trachea with a bougie
 - Attempt aborted due to a change in patient condition (e.g. worsened hypoxemia, hypotension, bradycardia, vomiting, bleeding)
 - Technical failure of the laryngoscope (e.g. battery, light source, camera, screen)
 - Other
- Operator-reported aspiration

Exploratory safety outcomes are as follows:

- Esophageal intubation
- Injury to the teeth

Exploratory clinical outcomes are as follows:

- ICU-free days in the first 28 days
- Ventilator-free days in the first 28 days
- 28-day all-cause in-hospital mortality

Sample Size Estimation

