The minimum clinically important difference in successful intubation on the first attempt that would be needed to justify routine use of a video laryngoscope rather than a direct laryngoscope in the ED and ICU is uncertain. The current trial is designed to detect a 5% absolute difference between groups in the incidence of successful intubation on the first attempt. An absolute difference of 5% in successful intubation on the first attempt is similar to or smaller than the difference used in the design of prior airway management trials and is considered by airway management experts to be clinically meaningful. 21,28,38,39 Assuming (1) an incidence of successful intubation on the first attempt of 80% in the direct laryngoscope group, (2) 90% statistical power, (3) a two-sided alpha of 0.05, and (4) enrollment at 16 sites with an intra-cluster correlation for the primary outcome of 0.05, we calculated that detecting a 5% absolute increase in the incidence of successful intubation on the first attempt would require enrollment of 1,920 patients (960 per group). Anticipating missing data for up to 4% of enrolled patients, we will plan to enroll a total of 2,000 patients (1,000 per group).

Data and Safety Monitoring Board (DSMB) and Interim Analysis

A DSMB composed of experts with backgrounds in emergency medicine, pulmonary and critical care medicine, anesthesiology, bioethics, and biostatistics has overseen the design of the trial and is monitoring its conduct. The DSMB will review a single interim analysis prepared by the study biostatistician at the anticipated halfway point of the trial, after enrollment of 1,000 patients. The stopping boundary for efficacy was pre-specified as a P-value of 0.001 or less, using a chi-square test, for the difference in the incidence of the primary outcome between groups. This conservative Haybittle—Peto boundary was selected to allow the final analysis to be performed using an unchanged level of significance (P < 0.05). The DSMB retains the authority to stop the trial at any point, request additional data or interim analyses, or request modifications of the study protocol to protect patient safety. Trial safety monitoring and handling of adverse

events are described in detail in the supplementary file, section 5. Patient privacy and data storage details are listed in the supplementary file, section 6.

Statistical Analysis Principles

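### Does leaving the effect measure for the number of laryngoscopy attempts open risk an uninformative difference in medians?

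*SAP*

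**What the plan says.** The SAP lists "Number of laryngoscopy attempts" among its exploratory procedural outcomes, without a variable type, cut-off or effect measure. Its section Analyses of Exploratory Outcomes covers every such outcome in one sentence: "We will calculate absolute risk differences or differences in medians between groups with the associated 95% confidence intervals". Neither measure is assigned to a particular outcome.

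Statistical Analysis Principles in the SAP deals with descriptive summaries. "For categorical variables, the number and proportion of patients will be presented"; continuous variables get a mean with standard deviation or a median with interquartile range, as appropriate. The attempt count is not placed in either class. Protocol 9.4.2 says only that exploratory outcomes will be compared by intention to treat.

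Two further places fix what the count can look like. Protocol 7.2.1 defines first-attempt success as "placement of an endotracheal tube in the trachea with a single insertion of a laryngoscope blade into the mouth", together with a single tube insertion or a single bougie insertion followed by a single tube insertion. Sample Size Estimation in the SAP assumes "an incidence of successful intubation on the first attempt of 80% in the direct laryngoscope group" and an absolute increase of 5 points with video.

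**The concern.** For most exploratory outcomes the choice between the two measures makes itself: a risk difference for esophageal intubation, dental injury and death, and a difference in medians for duration. The attempt count is less obvious. A risk difference needs a category such as two or more attempts, and the SAP names none. A reader could therefore expect a difference in medians.

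That measure would fail here. Most patients have the value 1, so the median is 1 in both arms over any plausible range. The result would be 0 with a zero-width interval, which could be misread as precise evidence that repeated laryngoscopy does not differ. The SAP says that analyses of this kind will emphasise effect sizes with 95% confidence intervals, and such an interval would defeat that aim. The trial is also unblinded, so a cut-off chosen late could be questioned.

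**Working it through.** The plan gives no figure for this outcome, so there is none to reproduce. The check needs only the planning rates and the group size.

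**Inputs**
- First-attempt success: 80% direct, 80% + 5 points = 85% video (SAP, Sample Size Estimation).
- Group size: 1,000 per arm; 1,920 / 0.96 = 2,000 in total, which agrees with the plan. Whether 1,920 follows from the stated power inputs is a separate question that does not bear on this one.
- Attempts are taken as the number of times the blade entered the mouth, as recorded under Protocol 7.1 and SAP Data Collection.
- f, the share of first-attempt failures that need a second blade insertion. The documents do not give it; the range 0.25 to 1 is an assumption.

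**Step 1: the medians.** Every first-attempt success has exactly one blade insertion, so P(count = 1) is at least 0.80 (direct) and 0.85 (video). With 1,000 patients a sample median exceeds 1 only if 500 or fewer have the value 1:
- P(Bin(1000, 0.80) ≤ 500) = 4.1 × 10⁻⁹⁹
- P(Bin(1000, 0.85) ≤ 500) = 1.9 × 10⁻¹⁴⁸

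The difference in medians is 1 - 1 = 0. In 2,000 simulated trials it was 0 every time, and the bootstrap interval was 0 to 0 in all 100 trials that were resampled. With 16 sites and an intra-cluster correlation of 0.05, none of 5,000 simulated trials had a median above 1 in either arm.

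**Step 2: how far this extends.** At 68% against 70%, the rates that the SAP introduction quotes from the largest earlier trial, the result is again 0 (0 to 0). At 60%, P(Bin(1000, 0.60) ≤ 500) = 1.0 × 10⁻¹⁰, so even 60% against 85% gives 0 (0 to 0). The median moves only when about half of an arm needs more than one insertion.

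**Step 3: the other permitted measure.** For two or more attempts, the risk is 0.20f (direct) and 0.15f (video). The risk difference is (0.15 - 0.20)f, with Wald interval ± 1.96 × √[p₁(1 - p₁)/1000 + p₀(1 - p₀)/1000]. At f = 1 the half-width is 1.96 × √[(0.1275 + 0.16)/1000] = 3.32 points.

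| f (assumed) | Direct | Video | Difference, points (95% CI) |
|---|---|---|---|
| 1 | 20.0% | 15.0% | -5.00 (-8.32 to -1.68) |
| 0.75 | 15.0% | 11.25% | -3.75 (-6.71 to -0.79) |
| 0.5 | 10.0% | 7.5% | -2.50 (-4.97 to -0.03) |
| 0.25 | 5.0% | 3.75% | -1.25 (-3.04 to 0.54) |

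With 960 evaluable per arm the intervals are -8.39 to -1.61 at f = 1 and -5.03 to 0.03 at f = 0.5.

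**Step 4: what the SAP sentence already has to do.** The same sentence covers the reason for first-attempt failure, which has six unordered categories, no median and no cut-off. It can work there only as a risk difference for each category. That reading is equally open for attempts grouped as 1, 2, and 3 or more.

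**Step 5: overlap with the primary outcome.** At f = 1 the risk difference for two or more attempts is the primary result with its sign reversed. At lower f it adds the distinction between failures resolved under the same blade insertion and those that were not, but it shrinks and the interval reaches zero.

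**The case for a change.** The strongest case for acting is that the gap is real, one of the two permitted measures is certain to be empty, and a sentence would close it at no cost. The blade counts are already recorded. Naming the cut-off in advance would also settle whether the comparison counts as a priori under Protocol 9.4.

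The arithmetic in that case stands in full, and so does the observation that the SAP leaves the measure open. What does not stand is the step from there to a faulty result. Nothing in the SAP steers this count to medians. Nor are medians the ready-made choice they seem: the sentence asks for a 95% interval and names no method for one, so both measures leave something to the analyst. The worry about a late cut-off is slight, since more than one attempt is the natural division of a count that starts at 1, and Protocol 9.4 labels analyses requested after enrollment as post hoc. A shift would also be visible in the planned tabulation by group if the count were shown as proportions or as a mean, though not as a median with interquartile range.

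**Conclusion.** No change to the plan is needed. The SAP leaves out a detail that an analyst would fill sensibly. Once both medians are seen to be 1, the count would be tabulated as 1, 2, and 3 or more, with the risk difference that the SAP already allows. Naming that measure would select from the plan rather than alter it.

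The consequence is small in any case. The outcome is exploratory, the raw counts are kept, and the main contrast of one against more than one blade insertion is largely contained in the primary outcome, which gets its own difference in proportions, interval and p value. If medians were used after all, the loss would be one exploratory interval, for an expected difference between -1.25 and -5.0 points over the assumed range of f.

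This rests on reading attempts as blade insertions and on single-insertion shares well above one half. The second holds at the planning rates and at the lowest rates the SAP quotes.

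A neighbouring wording difference changes nothing either. The protocol's Trial Summary has "Number of attempts to cannulate the trachea with a bougie Number of attempts to cannulate the trachea with an endotracheal tube" as two items, whereas Protocol 7.2.3 has "Number of attempts to cannulate the trachea with a bougie or an endotracheal tube" and the SAP has "Number of attempts to cannulate the trachea with a bougie or endotracheal tube". The two full lists agree with each other, and bougie and tube insertions are recorded separately, so either presentation remains possible.
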